In the absence of a CL, the ocular surface is covered by a complex bilayer of tears composed of the aqueous/mucin layer and the lipid layer.⁸ The aqueous/mucin layer directly interacts with the ocular surface, a layer that primarily serves to hydrates the eye.⁸ This layer is covered by an external lipid layer, which can be further divided into a polar lipid layer, which serves as an interphase between the aqueous/mucin layer and the nonpolar lipid layer, which interacts with the external environment and serves as a barrier to tear evaporation.⁸ When a CL is applied to the eye, this ~3 µm thick layer of tears is divided into a pre- and post-CL tear layer, which likely disrupts tear homeostasis.^{7,9} Soft CLs are also known to quickly absorb tear lipids, which has the potential to deplete tear lipids needed to maintain a healthy ocular surface.¹⁰ This theory is supported by how lipids deposited on CLs have been associated with CLD.¹¹ CLs them self are also associated ocular surface changes that likely induced the two primary forms of dry eye (aqueous deficient and evaporative dry eye).¹² Together, these tear factors along with the many other precipitating elements associated with CLD likely result in the characteristic decreased comfort and wear times associated with symptomatic CL wear.⁷

One first-line treatment for CLD is CL rewetting/lubricating drops.¹³ The U.S. Food & Drug Administration (FDA) defines rewetting/lubricating drops in their *Premarket Notification (510(k)) Guidance document for Contact Lens Care Products* as “an in-eye solution for use with CLs” that contains “one or more active ingredients (e.g., ophthalmic demulcents) in sufficient concentration to alleviate symptoms of discomfort from CL wear by physical means.”¹³ Clinicians also commonly use artificial tears off label for treating CLD and the dry eye associated with CLs because new artificial tear formulations have the potential to outperform the available CL rewetting drops.¹⁴ The FDA separately classifies artificial tears in their *Ophthalmic Drug Products for Over-the-Counter Human Use* monograph as topical drops that contain specific types of demulcents or emollients.¹⁵ While off-label, McDonald et al. have previously shown that using a common artificial tear, Systane Ultra, before and after CL use is an effective means for treating daily disposable CL wears who have CLD.¹⁴ Recently, a new formulation of artificial tears, Systane Complete, was released to the market. Systane Complete is a unique formulation that has combined elements from both Systane Ultra (indicated for aqueous deficient dry eye) and Systane Balance (indicated for evaporative dry eye) to create an artificial tear with an indication for aqueous deficient, evaporative, and mixed (both aqueous deficient and evaporative) dry eye. Thus, the Research Goals of this study are to determine in a randomized clinical trial if Systane Complete is able to effectively improve the symptoms and the quality of life of CLD suffers.

II. SPECIFIC AIM

We plan to accomplish our Research Goals by pursuing the following specific aims and testing the associated hypotheses:

Aim 1: Determine if Systane Complete is able to alleviate CLD in daily disposable CL wearers.
Hypothesis: Subjects who are randomized to the Systane Complete treatment group will have a statistically significant improvement in ocular surface symptoms (Contact Lens Dry Eye Questionnaire-8) compared to subjects who are randomized to the no treatment group.

Aim 2: Determine if Systane Complete is able to improve the quality of life of daily disposable CL wearers. Hypothesis: Subjects who are randomized to the Systane Complete treatment group will have a statistically significant improvement in their University of Michigan Vision Correction Quality of Life (UM-VCQoL) Questionnaire scores compared to subjects who are randomized to the no treatment group.

III. STUDY DESIGN

Subjects

This two-week, two-visit study will be conducted at the University of Alabama at Birmingham (Birmingham, AL, USA), Southern College of Optometry (Memphis, TN, USA), and Lindenhurst Eye Physicians & Surgeons, PC (Amityville, NY). Subjects will be recruited from each site via clinic records, postcards, email, social network postings (i.e., Facebook), and fliers. Adult (>18 years) daily disposable CL wearers who have 20/30 visual acuity or better and who self-report CLD will be recruited for this study. Other CL modalities/wear schedules (e.g., two week and monthly replacement CLs, gas permeable CLs) and non-compliant daily disposable CL users (must replace CLs daily) will be excluded to avoid any potential confounders associated with CL care systems. Subjects will be screened with the Contact Lens Dry Eye Questionnaire (CLDEQ)-8, and subjects who have CLD (CLDEQ-8 scores ≥ 12) will be enrolled in the study.¹⁶ Subjects will be excluded if they have known systemic health conditions that are known to alter tear film physiology (e.g., primary and secondary Sjögren's syndrome), have a history of ocular surgery within the past 12 months, have a history of severe ocular trauma, active ocular infection or inflammation, are currently using Accutane or ocular medications, or if they are pregnant or breast feeding.¹⁷ Subjects with a condition or in a situation, which in the examiner's opinion, may put the subject at significant risk, may confound the study results, or may significantly interfere with their participation in the study will be excluded. Subjects with non-Sjögren's dry eye disease and subjects who have mild corneal scarring (no corneal elevations changes) will be allowed to participate. Subjects who currently use artificial tears will be allowed to participate, though they will be required to not use artificial tears for at least 24 hours before the baseline study visit and during the study.

Randomization & Masking

This will be a prospective, single masked, randomized, clinical trial, which will be registered with ClinicalTrials.gov. Subjects who meet all study criteria will be enrolled and randomized into the study. Subject randomization will be organized by the data coordinator ([name], MS, PhD) and will follow the general guidance provided by Pucker et al. and the Cochrane Eye and Vision group.¹⁸ [name] will create a randomization schedule utilizing blocking (given the small sample size) and stratification by site to maximize the likelihood that study participants will be equally distributed between the treatment groups and by site. Subject group assignments will be concealed in numbered envelopes and distributed among the sites. After a subject is enrolled in the study and after the masked examiner has left the examination area, the unmasked study coordinator will open the envelope, place the subject in the correct group (artificial tears vs. no treatment) and educate the subject about it. The contents of the artificial tear bottle will be concealed. The unmasked study coordinator will educate the subject how to use the artificial tears (2x/day in each eye; once 10 minutes before and once directly after CL wear), and they will instruct the subject to not divulge any information related to their assigned group to the masked examiner. The study subjects will be instructed to not use other artificial tears or rewetting drops during the study.

Sample Size

CLDEQ-4 scores (Rasch validated version; max score of 18) will serve as the primary outcome for judging if Systane Complete is able significantly improve CL comfort.¹⁹ Data from Pucker et al. suggests that the average CL wearer has a mean CLDEQ-4 score of 7.6 ± 3.8 .¹⁹ A 4-point difference in CLDEQ-4 scores will be considered a meaningful improvement in CL comfort. Therefore, 19 subjects per group will be needed to determine if there is no difference in CL comfort between the Systane Complete and the no treatment groups at the two weeks visit (power = 90%; alpha = 0.05). After adjusting for 20% dropout, a total sample size of 46 subjects (16 subjects/site) will be needed to determine if there is a statistical difference in CL comfort scores between subject groups.

The University of Michigan Vision Correction Quality of Life (UM-VCQoL) Questionnaire will serve as the primary outcome for judging if Systane Complete is able to improve a symptomatic CL wear's quality of life.²⁰ McAlinden and Lipson found with this questionnaire that daily disposable CL wearers had a mean OCL-QoL score of 59.86 \pm 4.51.²⁰ A 5-point difference in OCL-QoL score will be considered a meaningful improvement in a patient's quality of life. Therefore, 18 subjects will be needed to determine if there is no difference in quality of life between subjects randomized to the Systane Complete and the no treatment groups at the two-week visit (power = 90%; alpha = 0.05). After adjusting for 20% dropout, a total sample size of 44 subjects (15 subjects/site) will be needed to determine if there is a statistical difference in CL comfort scores between subject groups. Given the larger sample size requirements for the CLEDQ-4, this study will plan to enroll 46 subjects (16 subjects/site).

Surveys and Clinical Tests

Clinical measurement will be obtained from both eyes of each subject and testing will be performed in the below order. Testing order was designed to sequentially administer the least invasive to most invasive test. This methodology will ensure that a previous procedure will have a minimal effect on all subsequent assessments.²¹ Subjects will be asked to report to the study without their CLs on to minimize the effect of CL removal on the study outcomes. Steps 1 through 9 will be completed by the masked examiner.

Visit 1

1. Subject History, Eligibility, Informed Consent: Subjects will be asked to repeat the screening survey at the study visit to verify that they are still eligible for the study. All subjects will be screened with the CLDEQ-8 to verify that they are symptomatic CL wearers (CLDEQ-8 scores \geq 12); the subjects will be specifically asked to think about the survey questions as if they were thinking about their end of day CL comfort. All relevant ocular, systemic, and surgical history will be gathered via a questionnaire developed by the investigators. This question will also ask about current artificial tear usage (brand, dosage, duration of use). Subjects will also be asked provide the study doctor with a valid CL prescription to verify that the subject is wearing daily disposable CLs. Non-eligible subjects will be dismissed at this time or rescheduled depending upon the reason for ineligibility. Eligible subjects will be enrolled, consented, and requested to sign a privacy document.

2. Questionnaires: All subjects will be asked to complete the Standardized Patient Evaluation of Eye Dryness (SPEED) because it is a validated dry eye symptoms questionnaire that asks about the most common dry eye symptoms.²² Subjects will also be asked to complete the University of Michigan Vision Correction Quality of Life questionnaire because it is a validated quality of life survey for CL wearers.²⁰

3. Visual Acuity: The subject's visual acuity will be measured with a Bailey-Lovie high-contrast (logMAR) chart or equivalent. If the patient is unable to read the 20/40 letters (0.3 logMAR), the investigator will pinhole over the patient's unaided or presenting refractive error correction (glasses) to determine the subject's visual potential.

4. Slit-Lamp Biomicroscopy: The investigator will use a slit-lamp biomicroscope to document normal and/or remarkable findings of the anterior eye structures: eyelashes (blepharitis), eyelids, conjunctiva, and cornea. Eyelids will be graded based upon a grading scale that was developed by the investigators.

5. Tear Break-Up Time (TBUT): A sterile sodium fluorescein strip will be wet with sterile saline and applied to the superior bulbar conjunctiva. The subject will then be asked to position themselves within the slit-lamp biomicroscope and blink three times, and the subject will then be asked to keep their eyes open and to not blink for as long as possible. The investigator will use a stopwatch to determine the number of seconds between the last blink and first break in the tears as viewed with a cobalt blue light and a yellow filter. The subject will then be allowed to blink normally for ten seconds before repeating the procedure. Each eye will be tested in triplicate, and the mean of each eye will be used in analysis.

6. Corneal Staining: A sterile sodium fluorescein strip will be wet with sterile saline and applied to the superior bulbar conjunctiva. After waiting for one-minute, corneal staining will be assessed with a cobalt blue light and a yellow filter. The CCLRU 0 to 4 grading scale will be used in 0.5 increments.²⁴

7. Schirmer's Test I: Tear volume will be assessed with a Schirmer's Test. In brief, the strip will be placed at the temporal third of the lower eyelids. The subject will then be asked to close their eyes for five minutes. The length of wetting will then be measured and recorded in mm.

8. Meibomian Gland Expressibility & Quality: The lower eyelid will be slightly everted to determine if there are any visibly obstructed glands. The central 8 meibomian glands will then be expressed with the investigator's finger by placing it about one millimeter below the inferior lash line and applying light pressure for 15 seconds. These metrics will be graded with the grading scales from Meadows and colleagues.²⁵

9. Exiting Visual Acuity: Visual acuity will be measured as described above.

10. Randomization: The masked examiner will leave the room, and the unmasked study coordinator will perform the randomization protocol described above. The unmasked study coordinator will then provide the subject with their predetermined group, educate the subject how to follow their study group assignment, and schedule the subject for their two-week outcome visit.

11. Subject Compliance: Subjects will be given a daily log to record the time of day when they use the eye drops. Subjects will be asked to record the time when they applied their CLs, removed their CLs, and the number of hours their CLs were comfortable. They will also be asked about their perceived perception of the eye drops (same, better, worse).

Visit 2

1. Repeat Visit 1 Tests: The masked examiner will administer the CLDEQ-8 and repeat procedures 2 through 9 as described above.

2. Study Completion: The masked examiner will leave the room, and the unmasked study coordinator will reveal the study details to the subjects (Systane Complete was being studied). The subject will be compensated for their time commensurate with each site's hourly rate, and they will be released from the study at this time.

Data Entry/Management

Surveys and all data will be collected via a secured web service (<https://www.qualtrics.com/>) at the time of the study visit. The online survey instrument will be designed on Qualtrics software. All data will be stored on Qualtrics servers, which meet the Health Insurance Portability and Accountability Act (HIPAA) standards and are secured against both physical and digital intrusion. Qualtrics will not be able to access subject's responses unless a request is made by the Data Coordinating Center to Qualtrics for assistance that would require their involvement with the data. All access is password protected, and data will only be stored electronically.

Risk to subjects, including a breach of confidentiality, is mitigated by the security measures utilized by Qualtrics. Physical access to the servers storing survey results is protected by a 24-hour security team, keycard and biometric authentication, digital surveillance, internally located server housings, and backup power generation. Data are also protected digitally by three mirrored Network Operations Centers, which monitor both local and regional networks including: points of presence, telecom facilities, routers, servers, and customer's infrastructure. Data are backed up at different locations in the compound via replication services, and nightly hard copies are generated and stored in a secure location. Workstations located inside the compound do not allow for remote access and do not contain any third-party software.

Data Analysis

[name], MS, PhD, Professor and Vice Chairman in the Department of Epidemiology at the University of Alabama at Birmingham, will perform the statistical analyses. All data will be analyzed with SAS Version 9.4 (SAS; Cary, NC, USA). The intention to treat analysis method will be employed. The treatment groups will be compared with respect to demographic and baseline clinical characteristics to ensure that the randomization was successful. T- and chi-square tests will be used when comparing continuous and categorical variables, respectively. If the assumptions of these tests cannot be met suitable alternative

statistical tests (e.g., Wilcoxon Rank Sum Test, Fisher's Exact Test) will be used instead. For the comparison of the primary outcome measures (CLDEQ-4 and UM-VCQoL scores), generalized linear models will be used with the follow-up measurement as the dependent variable and treatment group and baseline measurement used as independent variables. While we do not anticipate any differences between the treatment groups, this method ensures that any comparison between the treatment groups will be independent of even minor differences at baseline. Additionally, these models can account for potential differences between the treatment groups with respect to other characteristics, though we do not anticipate any such differences.

Training of Study Personnel

Prior to enrolling any subjects all examiners will meet at the Southern College of Optometry to complete protocol training developed by [name], OD, PhD. This full investigator meeting will ensure that all study investigators are performing the procedures in the same manner. Investigators will also be required to complete an online proficiency test. Data from each investigator's first subject will also be monitored by [name], MS, PhD for quality control before sites are allowed to enroll additional subjects.

.
.
.
.
.
.
.
.

VI. Conclusions

This project will be the first to evaluate the effectiveness of Systane Complete for the treatment of CLD in a rigorous and controlled manner. This work will also provide some of the first data on the impact of artificial tears on a CL wearer's quality of life. Ultimately, after completion of this study, clinicians will have the information needed to determine if Systane Complete is a suitable off-label treatment for patients who suffer from CLD

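### Enrolling 46 does not cover the plan's own 20% dropout for CLDEQ-4: about 36.8 remain against the 38 required, and 48 would be needed (small effect on power)

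*Combined protocol and SAP*

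**What the plan says.** The combined protocol and SAP sizes the trial in section III (Study Design), under Sample Size.

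- **CLDEQ-4, target at follow-up.** "Therefore, 19 subjects per group will be needed" for the comparison of the Systane Complete and "no treatment groups at the two weeks visit (power = 90%; alpha = 0.05"). The inputs are an SD of 3.8 and this difference: "A 4-point difference in CLDEQ-4 scores will be considered a meaningful improvement in CL comfort".
- **CLDEQ-4, enrolment.** "After adjusting for 20% dropout, a total sample size of 46 subjects (16 subjects/site) will be needed".
- **Quality of life.** The target is 18 subjects, followed by: "After adjusting for 20% dropout, a total sample size of 44 subjects (15 subjects/site) will be needed".
- **Operative figure.** CLDEQ-4 has the larger requirement, so "this study will plan to enroll 46 subjects (16 subjects/site").

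The Subjects subsection names three sites. Under Data Analysis, the primary comparison adjusts for baseline: "generalized linear models will be used with the follow-up measurement as the dependent variable and treatment group and baseline measurement used as independent variables".

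**The concern.** The 19 per group is tied to the two-week visit, so it is the number that must remain after losses. An enrolment figure adjusted for 20% dropout should leave at least 38 subjects when 20% of those enrolled are lost, and 46 does not. CLDEQ-4 is also the outcome that sets enrolment, so no larger requirement elsewhere absorbs the shortfall.

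At stake is whether the stated enrolment delivers the stated 90% power under the plan's own assumptions. The validity of the comparison is not in question.

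**Working it through.** **Inputs.** All are from the Sample Size subsection: difference 4 points, SD 3.8, alpha 0.05, power 90%, dropout 20%, total 46, 16 per site. Two groups of equal size are taken from the randomization text, and three sites from the Subjects subsection. Sidedness is not stated. Two-sided is assumed because it reproduces the plan's 19, whereas one-sided gives 16.

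**1. Reproduce the base figure.** n per group = 2(1.960 + 1.2816)² × 3.8²/4² = 18.97, so 19 per group and 38 in total. This matches the plan.

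**2. Reproduce the enrolment figure.**

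| Outcome | Needed | × 1.2 | ÷ 0.8 | Printed |
|---|---|---|---|---|
| CLDEQ-4 | 38 | 45.6 → 46 | 47.5 → 48 | 46 |
| Quality of life | 36 | 43.2 → 44 | 45 | 44 |

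Both printed totals fit multiplication by 1.2. For quality of life, the 18 subjects are read as 18 per group: 2(1.960 + 1.2816)² × 4.51²/5² = 17.10, so 18 per group and 36 in total.

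**3. Test the enrolment figure.**

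- 46 × 0.8 = 36.8, below 38.
- 48 × 0.8 = 38.4, above 38.
- Dropout tolerated with 46: 1 − 38/46 = 17.4% (8 losses).
- Dropout tolerated with 48: 1 − 38/48 = 20.8% (10 losses).
- Quality of life with 46 enrolled: 36.8 remain against 36 needed, so there is no shortfall.

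If each subject is lost independently with probability 20% (an assumption), the number remaining is Binomial(N, 0.8). The chance of keeping at least 38 is 41% for N = 46 and 64% for N = 48.

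**4. Effect on CLDEQ-4 power, unadjusted.** The normal approximation is power = Φ(4/[3.8 × √(1/n₁ + 1/n₂)] − 1.960). The t-test values are from the noncentral t distribution.

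| Evaluable | Normal approximation | t-test |
|---|---|---|
| 19 and 19 | 90.05% | 88.4% |
| 19 and 18 | 89.3% | 87.5% |
| 18 and 18 | 88.5% | 86.6% |

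By the approximation that gives the plan's 19, the loss is 0.8 to 1.6 points. An SD of 3.7 instead of 3.8 would give 90.0% at 18 and 18, so the loss is within the uncertainty of the inputs.

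**5. Effect of the planned baseline adjustment.** Replace the SD with 3.8 × √(1 − r²), where r is the correlation of baseline and follow-up scores. The documents do not give r. By the normal approximation, 90% is restored when r reaches about 0.16 (19 and 18) or 0.23 (18 and 18). Over an assumed range at 18 and 18:

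| r | 0.2 | 0.3 | 0.4 | 0.5 |
|---|---|---|---|---|
| Power | 89.7% | 91.2% | 93.1% | 95.4% |

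**The case against.** The strongest reply is that the plan already prints 16 per site, and 16 × 3 = 48. If every site fills its target, the shortfall disappears. That is true, but the total is stated as 46 twice, the second time as planned enrolment. The per-site figures look like rounded quotients: 46/3 = 15.33 gives 16, and 44/3 = 14.67 gives 15. This is an inference, since the plan does not explain them. At best the same sentence carries two totals, and only one meets the target.

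A second reply is that no inflation formula is given, and that 46 allows 8 losses, which is 21% of the 38 required (8/38). This works only if the dropout rate is taken as a share of those who must remain. The usual reading is a share of those enrolled, and on that reading 46 falls short.

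A third reply is that the effect is negligible. This largely stands. The loss is 0.8 to 1.6 points, and a modest baseline correlation would remove it, although the plan does not give one. It limits the point to a minor one but does not make the sentence correct.

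It is also fair to say that 48 is no guarantee. A t-test needs 20 per group for 90% power, hence 40/0.8 = 50 enrolled without baseline adjustment. Even with 48, under independent losses, the chance of ending below 38 is 36%. The case for 48 is only that it meets the plan's own target under its own method and expected dropout.

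**Conclusion.** The point holds and is minor. The stated total of 46 does not deliver what its sentence claims: at 20% dropout it leaves 36.8 evaluable against 38 required, and 48 is the smallest total that meets the requirement. Unadjusted CLDEQ-4 power is then about 89% rather than 90% by the plan's approximation, and the planned baseline adjustment may make up the difference.

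The shortfall itself rests only on the plan's figures, with dropout read as a share of those enrolled. The power figures also assume a two-sided test, the stated SD and difference, and the normal approximation. The recovery by adjustment depends on a correlation that the documents do not supply. The explanation that the plan multiplied by 1.2 is inferred from the printed totals, and the conclusion does not depend on it.

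**What to change.** In both places under Sample Size where 46 appears, state the total as 48, with the derivation 38/0.8 = 47.5, rounded up. This is 24 per group and agrees with 16 per site at three sites.

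If 46 is kept, say that it supports 19 per group only up to about 17% dropout, and that at 20% dropout unadjusted power is about 89% by the plan's approximation. Reconcile the per-site figure with whichever total is chosen.

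Either way, add that 19 per group and 90% power come from the normal approximation to a two-sided test, if two-sided was intended.

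The quality-of-life total does not need to change, because CLDEQ-4 sets enrolment. Dividing by 0.8 there would give 45 instead of 44, and printing 45 would keep the two paragraphs on one rule.

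The cost is a wording change if sites are already recruiting to 16 each. If 46 is the real recruitment target, it is two more subjects. Outcomes, design and analysis are untouched.

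### Both eyes are measured but subjects are randomized: does the missing rule for combining the two eyes put the analysis at risk?

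*Combined protocol and SAP*

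**What the plan says.** Under Randomization & Masking the unit is the subject: "Subjects who meet all study criteria will be enrolled and randomized into the study". One assignment covers both eyes.

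Surveys and Clinical Tests states that "Clinical measurement will be obtained from both eyes of each subject". Visit 1 then lists the procedures. For tear break-up time (step 5) the rule is "Each eye will be tested in triplicate, and the mean of each eye will be used in analysis". The other steps say how a sign is recorded or graded, for example "The CCLRU 0 to 4 grading scale will be used in 0.5 increments" for corneal staining and "Eyelids will be graded based upon a grading scale that was developed by the investigators" for the lids. They do not say how right and left eyes are brought together. At Visit 2, "The masked examiner will administer the CLDEQ-8 and repeat procedures 2 through 9 as described above".

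Data Analysis provides for one comparison that plainly includes the signs: "The treatment groups will be compared with respect to demographic and baseline clinical characteristics to ensure that the randomization was successful". It names t-tests and chi-square tests. Where their assumptions fail, it allows suitable alternatives, giving the Wilcoxon rank sum and Fisher's exact tests as examples. The generalized linear model, with follow-up score regressed on group and baseline score, is stated for the two questionnaire outcomes, CLDEQ-4 and UM-VCQoL.

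**The concern.** Two eyes of one person tend to resemble each other, and here both receive the same assignment. The tear break-up sentence averages three readings within an eye and stops. Read literally, it sends two values per randomized subject into analysis. All four tests named in Data Analysis assume independent observations. An analyst who entered every eye as a separate record would overstate the information, obtain standard errors that are too small, and reject too often. Visual acuity, lid grade, staining, Schirmer wetting and the two meibomian measures have no rule at all.

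Two things would be at stake. A baseline table meant to show that randomization worked could flag imbalances that are not there. And because the unit is not fixed, it could be chosen after the data are seen: pooled eyes, each eye separately, or one value per subject.

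**Working it through.** **What the sample size rests on.** With two-sided alpha 0.05 and power 90%, z-values 1.960 + 1.282 = 3.242.

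- CLDEQ-4 (difference 4, SD 3.8): n = 2 × (3.8 × 3.242 / 4)² = 18.97, so 19 per group, as stated.
- UM-VCQoL (difference 5, SD 4.51): n = 2 × (4.51 × 3.242 / 5)² = 17.10, so 18 per group, as stated.
- Total: 38 × 1.2 = 45.6, so 46, as stated.

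Both inputs are questionnaire scores, one per subject. The number of eyes does not enter.

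**If both eyes were pooled as independent.** Let each eye have variance σ², fellow-eye correlation ρ, and n subjects per arm. The true variance of an arm mean over 2n eyes is σ²(1 + ρ)/(2n); the test takes it as σ²/(2n). So the standard error used is 1/√(1 + ρ) of the true one, and the actual two-sided error is 2 × [1 − Φ(1.96/√(1 + ρ))]. The documents give no ρ; 0.3 to 0.9 is assumed.

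| ρ | SE used / true SE | Actual error at nominal 5% | 76 eyes (19 per arm) are worth |
|---|---|---|---|
| 0.3 | 0.877 | 8.6% | 58.5 |
| 0.5 | 0.816 | 11.0% | 50.7 |
| 0.7 | 0.767 | 13.3% | 44.7 |
| 0.9 | 0.725 | 15.5% | 40.0 |

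Null simulations (40,000 trials per setting, 19 or 23 subjects per arm) agree: 8.6-16.2% for normal data, 8.0-16.0% for right-skewed data, and 7.9-15.5% by t-test for a skewed 0-4 grade in half steps.

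**False flags at baseline.** Count seven two-eye measures: acuity, lid grade, tear break-up time, staining, Schirmer, meibomian expressibility and meibomian quality. The expected number under sound randomization is 7 × 0.05 = 0.35. With pooled eyes it is 7 × 0.079 = 0.55 to 7 × 0.162 = 1.13. The count of seven is itself a choice, and the upper figure applies the highest rate to every measure.

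**The other readings the text allows.**

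- Right and left eyes tested separately: each test holds about 5%; the chance that at least one of the two is significant is about 7-10% per sign. Each standard error is √(2/(1 + ρ)) = 1.24 to 1.03 times that of the two-eye mean.
- Two eyes averaged first: 4.6-5.2% in simulation.

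**Where any of this could reach a conclusion.** Aim 1 is judged by the CLDEQ score and Aim 2 by the UM-VCQoL score. Each is a single number per subject and each primary model has one record per subject. Data Analysis specifies no follow-up test of a sign. It attaches no decision to the baseline p-values. It does say the primary models can account for other differences between the groups, but it does not make a baseline flag the trigger for doing so.

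**The case for a change.** The best case for a change is that a plan should lead two analysts to the same result, and here the one written rule stops at the eye. The baseline comparison is a committed analysis with a stated purpose, the named tests do not handle paired eyes, and a false imbalance might prompt an extra covariate in a primary model. A rule would take a few sentences and need no new data.

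The omission is real, at least in the visible text, and the inflation figures are correct on their condition. The rest carries less weight. The tear break-up sentence sits in a test procedure and reads most naturally as an instruction for reducing triplicate readings, not as a decision to count eyes as subjects. Independence is one of the assumptions of the named tests, so the clause on suitable alternatives already leaves room for a method that respects the pairing. A false flag would have no prescribed consequence. The worry about choosing the unit after seeing the data attaches to no stated efficacy test. Nor is there one correct rule to insist on: a two-eye mean, a designated study eye, or a model with subject as cluster would each serve. Averaging has its own cost, since it can dilute a change confined to one eye.

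**Conclusion.** The plan leaves the unit of analysis for two-eye signs unwritten; it does not specify a wrong analysis. The error of about 8-16% depends on an analyst pooling eyes as independent, which the plan never states, and on an assumed fellow-eye correlation of 0.3 to 0.9. Even then the effect is confined to a descriptive baseline check, at most about 0.8 additional expected false flags over seven measures (1.13 − 0.35 = 0.78), and to any follow-up comparison of signs that might be reported outside the stated analyses. The primary outcomes, their model, the 46-subject total and the answers to both aims are untouched. A statistician can be expected to fill this gap sensibly, so no change to the plan follows.
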